8.0 AGENT INFORMATION

8.1 Polatuzumab vedotin

Polatuzumab vedotin is FDA-approved for the treatment of adult patients with relapsed or refractory DLBCL, not otherwise specified, in combination with bendamustine and a rituximab product, after at least two prior therapies.

8.1.1 Other names

Polivy, DCDS4501A.

8.1.2 Description

Polatuzumab vedotin is an ADC that contains a humanized IgG1 anti-CD79b monoclonal antibody (MCDS4409A) and a potent antimitotic agent (MMAE) linked through a protease-cleavable linker. An average of 3.5 molecules of MMAE are attached to each antibody molecule.

Polatuzumab vedotin is approved by the FDA for the treatment of diffuse large B-cell lymphoma, relapsed or refractory, in combination with bendamustine and a rituximab product, after at least 2 prior therapies.

Please refer to the investigator brochure for a detailed description.

8.1.3 Mechanism of action

Polatuzumab vedotin targets the cell surface antigen CD79b which is expressed on mature B cells, with the exception of plasma cells. Following internalization, the ADC is cleaved by lysosomal enzymes to release MMAE and other potentially active catabolites. Free MMAE binds to the microtubule network and subsequently leads to cell cycle arrest and apoptosis.

8.1.4 Pharmacokinetics and Metabolism

ADC Vd:	3.15 L
MMAE protein binding:	71-77%
MMAE Metabolism:	Substrate of CYP3A4 and P-gp
ADC Total body excretion:	0.9 L/day
ADC Elimination half-life:	12 days
MMAE Elimination half-life	4 days

8.1.5 Toxicology

8.1.5.1 Expected human toxicities

See Section 6.1 for a detailed list of anticipated AEs.

8.1.5.2 Potential effects on fertility, pregnancy and lactation

Adverse effects on human reproduction and fertility are anticipated with the administration of polatuzumab vedotin based on the mechanism of action of the cytotoxic component of polatuzumab vedotin as a microtubule inhibitor. Given that MMAE, the cytotoxic component of polatuzumab vedotin, is a microtubule inhibitor targeting rapidly dividing cells and is a known teratogen, polatuzumab vedotin is expected to be teratogenic and embryotoxic.

It is not known whether polatuzumab vedotin can be found in sperm. Based on findings from animal studies, polatuzumab vedotin may impair male fertility. Individual patients seeking to preserve fertility should discuss the options available to them with their physicians prior to treatment initiation.

No clinical studies assessing the reproductive and developmental toxicity of polatuzumab vedotin have been conducted to date. It is not known whether polatuzumab vedotin can cross the placenta or cause harm to the fetus when administered to pregnant women or whether it affects reproductive capacity. Therefore, polatuzumab vedotin should not be administered to pregnant women.

It is not known whether polatuzumab vedotin is excreted in human breast milk. Because many drugs are excreted in human milk and because of the potential for harm to nursing infants, polatuzumab vedotin should not be administered to nursing mothers.

8.1.6 Formulation

Polatuzumab vedotin is provided in 140 mg, white to grayish-white lyophilized powder for reconstitution, in single-use vials.

8.1.7 Handling, storage, dispensing and disposal

Store refrigerated at 2°C to 8°C in original carton to protect from light. Do not use beyond the expiration date. Do not freeze. Do not shake.

For polatuzumab vedotin reconstitution, dilution, and storage of diluted solutions, please refer to the USPI.

Polatuzumab vedotin is a cytotoxic drug. Follow applicable special handling and disposal procedures.

8.1.8 Administration

Administer polatuzumab vedotin as an intravenous infusion only.

Polatuzumab vedotin must be administered using a dedicated infusion line equipped with a sterile, non-pyrogenic, low-protein-binding in-line or add-on filter (0.2- or 0.22-micron pore size) and a catheter.

Compatibility between polatuzumab vedotin and closed system transfer devices (CSTDs) or needle free transfer devices has not been assessed. If CSTDs or needle free transfer devices must be used to comply with site regulations, the site should be aware that their use may lead to the introduction of particles and may not allow the withdrawal of the labeled quantity of drug from the vial. Sites should perform a thorough visual inspection of the IV bag for particulates. In addition, sites must use a 0.2 or 0.22 µm polyethersulfone (PES) filter during infusion. The preparation should be discarded if particulates are observed in the IV bag.

Do not mix polatuzumab vedotin with, or administer as an infusion with, other medicinal products.

See Section 5.8.2 for administration guidelines.

8.1.9 Supplier

Polatuzumab vedotin will be supplied free of charge by Genentech.

8.1.10 Ordering

Sites will place orders for polatuzumab vedotin via the Genentech investigator initiated study drug supply request form.

Sites should place orders at least 2 weeks in advance.

8.1.11 Accountability

The investigator, or a responsible party designated by the investigator, must maintain a careful record of the inventory and disposition of the agent using a drug accountability log.

8.1.12 Destruction and Return

The investigator is responsible for keeping accurate records of the clinical supplies received from Genentech or designee, the amount dispensed to participants, and the amount remaining at the conclusion of the trial.

Any unused agent at the end of the study, expired agent, and damaged agent will be destroyed according to applicable federal, state, local and institutional guidelines and procedures.

Destruction will be documented in a drug accountability log.

8.2 Rituximab, Etoposide, Ifosfamide, and Carboplatin (R-ICE)

Agents contained in the R-ICE regimen are approved by the FDA for use in treating patients with multiple types of cancer. Please refer to the package insert for a detailed description.

8.2.1 Other names

Rituximab: Rituxan

Etoposide: VePesid, Etopophos, Toposar (VP-16)

Ifosfamide: Ifex

Carboplatin: Paraplatin

8.2.2 Description and mechanism of action

R-ICE is a standard chemo-immunotherapy regimen consisting of rituximab, etoposide, ifosfamide, and carboplatin. Rituximab is a CD20-directed cytolytic antibody. Etoposide is a topoisomerase inhibitor. Ifosfamide is a nitrogen mustard alkylating agent. Carboplatin is a platinum-based antineoplastic agent with a mechanism of action that interacts with DNA to inferfere with DNA repair.

8.2.3 Pharmacokinetics and Metabolism

Refer to respective package inserts for additional information.

Ifosfamide:

Half-life: Mean terminal t½ between 7-15 hours with single doses

Distribution: 0.64-0.72 L/kg

Protein binding: low Metabolism: Hepatic

Elimination: Urine (70-86%)

Ifosfamide is a substrate for both CYP3A4 and CYP2B6.

Carboplatin:

Half-life: Initial t½ is 1.1-2 hours. Post-distribution t½ is 2.6-5.9 hours

Distribution: 16 L Protein binding: None

Elimination: Urine (65-71%)

Etoposide:

Half-life: Initial t½ is 1.5 hours. Mean terminal t½ is 4 to 11 hours

Distribution: 7-17 L/m²
Protein binding: 94-98%

Metabolism: Hepatic via CYP3A4

Elimination: Urine (56%) within 120 hours; feces (44%) within 120 hours

8.2.4 Human Toxicity

See Sections 6.2 to 6.5.

8.2.5 Formulation

Refer to respective package inserts.

8.2.6 Storage

Rituximab, etoposide, ifosfamide, and carboplatin should be stored per their respective package insert.

8.2.7 Preparation and Handling

Rituximab, etoposide, ifosfamide, and carboplatin should be prepared and handled per their respective package insert and institutional standard.

8.2.8 Administration

See Section 5.8.3.

8.2.9 Supplier

Agents contained in the R-ICE regimen are commercially available and will be billed to patients and/or their third-party payer.

9.0 CORRELATIVE/ SPECIAL STUDIES

9.1 Research Sample Collection and Dispensation

9.1.1 Correlative tumor tissue

9.1.1.1 Time points of Collection

Baseline tissue: Archival tissue from diagnostic tumor biopsies will be retrieved and submitted post-enrollment.

NOTE: If unavailable, exceptions may be granted with the lead study PI approval.

If safe and feasible, submission of left-over tissue from a standard of care tumor biopsy (fresh core or excisional biopsy) for participants who progress/relapse during study is encouraged.

9.1.1.2 Guidelines for archival specimens

Using the formalin-fixed paraffin embedded (FFPE) tissue block, the following samples will be processed for correlative studies:

If tissue block is available submit:

6 paraffin scrolls measuring 10 μm thick placed into a tube and frozen at -80° C

AND

10 x 5 μm thick unstained slides

o If tissue block is unavailable submit:

20 x 5 µm thick unstained slides

9.1.1.3 Labeling of samples

Samples will be labeled with the COH protocol #, subject ID (issued by DCC), institution, date, time point of collection, and if applicable patient initials.

9.1.1.4 Sample shipment and receiving lab

Samples will either be taken to (COH only) or batch-shipped (non-COH sites) to COH Pathology Core. For all sites, please include the **Correlative Tissue form (Appendix E)** with your shipment.

Please note that samples should be **batch-shipped from non-COH sites on Monday to Wednesday** in time for receipt Tuesday to Friday. **Refer to Appendix F for tissue shipping details.**

9.1.2 Correlative blood

9.1.2.1 Overview and Time points

Peripheral blood will be collected prior to study treatment/procedures at the time points indicated in Table 9.1.2.1

Table 9.1.2.1 Overview of correlative blood studies

Time points of collection	Total volume collected	Tube type	Receiving laboratory	Type of analysis
 C1D1 C2D1 End of Salvage C1D1 of Consolidation End of Consolidation* At Progression/Relapse 	20 ml	Cell-free DNA BCT® (Streck)	APCF	ctDNA/MRD

APCF = COH Analytical Pharmacology Core Facility.

Cell-Free DNA BCT® (glass, 10 mL volume) tubes from Streck. Cat. No, as of April 2020, for a box of 100 tubes is: 218962.

^{*} For this time point, correlative blood will be collected at the safety visit (30 days post-).

9.1.2.2 Labeling of blood samples

Label tubes with COH protocol #, subject ID (issued by DCC), institution, date and actual time point of collection (e.g. C1D1 for Day 1 of Cycle 1), and if applicable patient initials.

9.1.2.3 Collection and post-collection guidelines

Refer to Table 9.1.2.3 for collection and post-collection instructions.

Refer to Appendix G and Appendix H for blood collection form and blood shipping guidelines, respectively.

 Table 9.1.2.3 Blood sample collection and post-collection instructions.

Tube Type	Collection details	Site of collection	Post-collection instructions
Cell-free DNA BCT® (Streck)*	1- Blood samples will be collected from an indwelling venous catheter or by venipuncture. Prevention of backflow: (Because cell-free DNA BCT® contain chemical additives) a. Keep patient's arm in the downward position during the collection procedure. b. Hold the tube with the stopper in the uppermost position so that the tube contents do not touch the stopper or the end of the needle during sample collection.	COH Only	Promptly deliver the blood samples to the APCF, [name].
	 c. Release tourniquet once blood starts to flow in the tube, or within 2 minutes of application. 2- Fill tube completely. 3- Remove tube from adapter and immediately mix by gentle inversion 8 to 10 times. 4- Do not freeze samples. Store samples at 18-25°C until shipment. 	Non-COH Sites Only	Ship to APCF laboratory. See Appendix H. Include with shipment: Blood sample collection form (Appendix G). Copy of latest CBC results (with differential) and date of test.

^{*} Tubes are stable when stored at 2-30°C through expiration date.

9.2 Laboratory Studies Performed

Please refer to Section 2.2.

10.0 STUDY CALENDAR

All assessments may increase in frequency as clinically indicated.

		Protocol therapy ^b																			
		Salvage PolaR-ICE ^C				Consolidation Pola ^d		Follow-up (~2 years)													
Protocol Activity	C1	C1 C2		(C3)		End of Salvage h	C1	C2 C3 (C4)	Safety	Active	Survival										
	Scr	D1 ^e	D1 ^e	D15 ^g	D1 ^e	D15 ^g	- 2 4.0	D1 ^e	D1 ^{e,f}	30-days post i	12 months & k	k									
Informed Consent	Х																				
Medical History	Х																				
Eligibility	Х																				
Registration	Х																				
Height	Х																				
Physical Exam	Х	x x	X		x		х	Х	Х	X											
& Vital signs ^m	_ ^					^	^	^	^	_ ^	^	^	^					,	^		
ECOG Status (Appx. A)	Х	х	х		Х		х	Х	Х	Х											
Con-med review	Х	Х	Х		Х		Х	Х	Х	Х											
AE Assessment	Х	Х	Х		Х		Х	Х	Х	Х											
Pregnancy ⁿ	Х	х	Х		Х			Х	Х												
CBC w/diff, plt & Serum chemistry ^p	хо	x	x		х		х	Х	х	x											
PT/INR and aPTT	Х																				
Correlative blood q		х	Х				Х	Х		(X)											
Correlative tumor tissue	x r		X s																		
Bone marrow biopsy/ aspirate	(X) ^u		x t																		

Protocol therapy b													
		Salvage PolaR-ICE ^C					Consolidation Pola ^d		Follow-up (~2 years)				
Protocol Activity	e Buing a C1	Screening ^a	C1	C	2	(C3)	End of Salvage h	C1	C2 C3 (C4)	Safety	Active	Survival
	Scr	D1 ^e	D1 ^e	D15 ^g	D1 ^e	D15 ^g		D1 ^e	D1 ^{e,f}	30-days post i	12 months & 24 months j	k	
PET-CT	Х			Х		Х				χV	χV		
Polatuzumab vedotin for Salvage		D1 of each cycle											
Rituximab		D1 of each cycle											
Etoposide		D1-3 of each cycle											
Carboplatin			D2 c	of each cy	/cle								
Ifosfamide (+Mesna)		D2 (Inpatient) or D1-3 (Outpatient) of each cycle											
Criteria to initiate Consolidation								Х					
Polatuzumab vedotin for Consolidation								Х	х				
Survival status												X	

- a. Screening activities to occur within 28 days prior to start of protocol therapy except for laboratory assessments and bone marrow biopsy.
- b. In the absence of treatment delay, each treatment cycle lasts 21 ± 3 days.
- c. All patients will receive 2 cycles of PolaR-ICE. Patients with PR after 2 cycles will receive an additional cycle of PolaR-ICE (3 cycles total). Patients with CR or SD after 2 cycles may receive an additional cycle of PolaR-ICE (3 cycles total) at the treating physician's discretion.
- d. Patients must meet the criteria to receive Consolidation Pola within timelines specified in Section 5.7.1. Patients who received 2 cycles of PolaR-ICE during Salvage will receive 4 cycles of Pola Consolidation. Patients who received 3 cycles of PolaR-ICE during Salvage will receive 3 cycles of Pola Consolidation. The maximum number of Pola-containing cycles of therapy is 6.
- e. Activities to be performed within 72 hours prior to initiation of the cycle.
- f. Evaluations performed within 14 days prior to start of Consolidation Day 1 may serve as Day 1 evaluations.
- g. Day 15 assessments have a ± 7 day window.

- h. End of salvage visit to occur within 30 days from last dose. Patients eligible for AHCT will then proceed to AHCT.
- i. The Safety 30 days post-last dose assessments to occur 30 (±7) days post-last dose or, if > 30 days elapsed since last dose, within 7 days after decision to end treatment. Expedited reporting will occur during this period. Safety follow-up may be extended until resolution/ stabilization of reportable AEs.
- j. For participants yet to progress, Active Follow-up will occur at 12 months (± 30 days) and 24 months (± 30 days) from the start of treatment until progression or the initiation of a new anti-lymphoma therapy.
- k. Participants who end Active Follow-up will enter Survival Follow-up. Survival assessment to occur bi-annually or as requested by the Study PI via medical record review, review of social security registry, or telephone call.
- I. Standard physical exam includes weight.
- m. Vital signs: heart rate, blood pressure, respiration rate, and temperature.
- Women of child bearing potential: Pregnancy serum or urine test. For the screening time point, pregnancy test must be performed within 7 days prior to start of protocol therapy.
- o. Screening laboratory assessments to be performed within 14 days prior to start of protocol therapy.
- p. Serum chemistry panel to include: glucose, Blood Urea Nitrogen (BUN), creatinine, uric acid, total protein, albumin, magnesium, bicarbonate, calcium, inorganic phosphorous, sodium, potassium, chloride, total bilirubin, alkaline phosphatase, ALT, AST, and LDH.
- Refer to Section 9.1.2.
- r. Archival tumor tissue to be submitted post-enrollment. Note: If unavailable, exceptions may be granted by the Study PI. Refer to Section 9.1.1.
- s. If safe and feasible, submission of left-over tissue from a standard of care tumor biopsy (fresh core or excisional biopsy) for participants who progress/relapse during study is encouraged. Refer to Section 9.1.1.
- t. Bone marrow biopsies will be performed only as clinically indicated, and to confirm CR.
- u. Bone marrow biopsy will be performed only as clinically indicated.
- v. CT in lieu of PET-CT is allowed if patient is in CR and CR was already confirmed by PET-CT.

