2.0 BACKGROUND

2.1 Introduction/Rationale for Development

2.1.1 Diffuse Large B-cell Lymphoma

Diffuse large B-cell lymphoma (DLBCL) is the most common lymphoma and accounts for 30-40% of newly diagnosed patients with non-Hodgkin lymphoma (NHL), representing the most common lymphoid neoplasm in adults.[9] DLBCL is considered as one of the aggressive type of NHL, with median age 70 years at diagnosis. Although the majority of patients with newly diagnosed DLBCL achieve long-term remissions with rituximab and multi-agent chemotherapy, approximately 30% of patients will experience relapse or progression. At the time of relapsed disease, the treatment approach is based on whether the patient is a candidate for autologous stem cell transplant (ASCT). In patients considered to be transplant eligible, the decision to proceed to ASCT is determined by the response to salvage treatment.[10, 11] The goals of salvage therapy are typically to minimize disease burden and induce remission, providing the best opportunity to benefit from consolidative ASCT.

Various multi-agent salvage regimens incorporating rituximab have been explored in DLBCL patients. A large randomized comparison of the most commonly used salvage regimens demonstrated the equivalence of rituximab combined with either ICE (ifosfamide, carboplatin, etoposide) or DHAP (dexamethasone, cytarabine, cisplatin).[8]

There were no significant differences overall between these regimens, and the combined results supported an overall response rate (ORR) of 63%, with 37% of patients achieving a complete remission (CR of 25%, unconfirmed CR of 12%). The median progression-free survival (PFS) was found to be approximately 1 year, with a 3-year event-free survival of 31% and 3-year overall survival (OS) of 50%. Patients with chemo-sensitive disease who achieved a CR or partial remission (PR) and had adequate stem cell collection were candidates to proceed to ASCT; only 50% of patients were able to undergo ASCT following salvage therapy. The most common reason to not proceed to ASCT was treatment failure to induce remission.

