5.11 Follow-Up

All participants who end protocol therapy will enter follow-up for 2 years.

NOTE: Assessments may be combined if the windows for the two visits overlap.

Follow-up is comprised of:

Safety Follow-up- 30 days post-last dose of protocol therapy.

- **Note** the period for safety follow-up will be extended until stabilization or resolution for all reportable AEs (per the agreement of the Study PI) and accompanying follow-up safety report.
- o **Response Follow-up-** for those who have yet to have disease progression.
- Survival Follow-up- for all participants who have progressed OR completed Active Response Follow-Up OR initiated a new anti-lymphoma therapy. This follow-up will be performed typically via medical record review. It will entail (a) Disease status (for those who have yet to progress) (b) Vital status (all participants).

Assessment time points and windows are detailed in Section 10.

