11.0 ENDPOINT DEFINITIONS/MEASUREMENT OF EFFECT

11.1 Assessment of Response

Lymphoma response/progression will be evaluated using 2014 Lugano Classification (see Appendix B). [38]

Disease assessment will be performed by PET-CT. For patients in CR, diagnostic quality CT is acceptable at the end of consolidation and during active Follow-up. Assessment with PET-CT is required to confirm CR. Patients with bone marrow involvement at baseline must have a bone marrow biopsy performed to confirm CR (if applicable). After CR, additional bone marrow biopsy is only required if clinically indicated. Additional necessary restaging studies including dedicated CT scans or MRI, are permitted at the investigator's discretion. PET-CT and CT results will be read by a radiologist at each study site and investigator response assessment will be performed.

For patients with progression of disease on imaging, it is strongly recommended that a confirmatory biopsy be obtained whenever possible.

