12.3 Sample Size and Accrual Rate

The minimum study accrual will be 4 patients, when both dose levels are found to be not tolerable during the safety lead-in portion. The expected total sample size for the study is 40 evaluable patients, assuming that dose level 1 (starting dose level) is safe and passes the first stage response evaluation in Phase 2, and safety lead-in patients are also evaluable for response. However if dose level 1 is not tolerable and dose level -1 is tolerable, the study will need to accrue up to 48 evaluable patients for the safety lead-in and phase 2 evaluations. Accounting for up to 10% inevaluable patients for unacceptable toxicity evaluation during Safety lead-in or inevaluable for response during Phase 2, the maximum accrual for the study is estimated to be 53 patients. Given that this is a multicenter study including high-volume DLBCL centers, we anticipate completing study accrual within 24 months.

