12.6 Statistical Analysis Plan

Patient demographics, baseline disease characteristics and prior treatment therapy will be summarized using descriptive statistics. For continuous variables, descriptive statistics such as number, mean, standard deviation, standard error, median (range) etc. will be provided. For categorical variables, patient counts and percentages will be provided.

CR rate after PolaR-ICE salvage therapy will be estimated by the proportion of response-evaluable patients achieving CR after 2 cycles of salvage therapy, along with the 95% exact binomial confidence interval. ORR after PolaR-ICE salvage therapy will be similarly estimated. PFS and OS will be estimated using the product-limit method of Kaplan and Meier along with the Greenwood estimator of standard error; 95% confidence interval will be constructed based on log-log transformation. Median PFS/OS will be estimated when

available. Observed toxicities of PolaR-ICE salvage therapy and Pola single-agent consolidation therapy will be summarized by type (organ affected or laboratory determination such as absolute neutrophil count), severity, and attribution.

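### No disease check is scheduled between months 12 and 24 for progression-free patients, so Kaplan-Meier PFS there is biased upward to the extent that progressions surface only at scans

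*Combined protocol and SAP*

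**What the plan says.** - **Scheduled disease checks.** The Study Calendar (Section 10.0) places PET-CT at screening, around Day 15 of salvage cycle 2 (and cycle 3 if given), and 30 days after the last dose. After that, for patients who have not progressed, "Active Follow-up will occur at 12 months (± 30 days) and 24 months (± 30 days) from the start of treatment". Section 11.1 adds that, for patients in CR, "diagnostic quality CT is acceptable at the end of consolidation and during active Follow-up".
- **Record review.** Footnote k of the calendar says "Survival assessment to occur bi-annually or as requested by the Study PI via medical record review", but this applies to patients who have ended Active Follow-up. Section 5.11 includes disease status in that review for those who have not yet progressed.
- **Unscheduled checks.** The calendar opens with "All assessments may increase in frequency as clinically indicated", and Section 11.1 permits further restaging at the investigator's discretion.
- **Endpoint and analysis.** Section 11.3 runs PFS from start of treatment to relapse, progression or death, censored at last follow-up. Section 12.6 uses Kaplan-Meier and says "Median PFS/OS will be estimated when" available. Neither section says how to date a progression first seen at a scheduled scan.
- **Historical anchor.** For earlier salvage regimens, Section 2.1.1 reports: "The median progression-free survival (PFS) was found to be approximately 1 year".
- **Length of follow-up.** Section 5.11 says "All participants who end protocol therapy will enter follow-up for 2 years". The synopsis gives participant duration as about 24 months and study duration as about 4 years.

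**The concern.** Kaplan-Meier treats each progression as occurring on its recorded date. If a progression at month 13 is first seen at the month-24 scan and recorded then, the curve stays flat for 11 months in which it should have fallen. The error always favours the regimen.

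The patients concerned are those still able to have a progression event, and they have the sparsest scheduled contact in that year. The only PFS anchor in the protocol, about 12 months, sits at the start of the gap. A regimen that improves on it would put the median inside the gap, where the estimate is least reliable. PFS after salvage, transplant and consolidation is a secondary objective, and in a single-arm trial readers will naturally set it beside published figures.

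**Working it through.** **1. The plan's own figure.** PFS has no stated sample size, event count or precision. The related stated figure is the study duration. Accrual takes 24 months (Section 12.3: "we anticipate completing study accrual within 24 months"). Adding 24 months from start of treatment gives 24 + 24 = 48 months, which reproduces the synopsis's 4 years.

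**2. Timeline.** Inputs: 21-day cycles, and consolidation starting at Day +30 to +75 after ASCT (the upper end only after consultation). Assumed: 21 to 60 days from the last salvage dose to ASCT. With two salvage cycles the last salvage dose is on Day 22, and the fourth consolidation dose comes 63 days after the first. Three salvage plus three consolidation cycles give the same total (43 + 42 = 22 + 63 = 85).
- Last dose: 22 + 21 + 30 + 63 = 136 days to 22 + 60 + 75 + 63 = 220 days, or months 4.5 to 7.2.
- Scan 30 days later: days 166 to 250, or months 5.5 to 8.2.
- Gap to month 12: about 4 to 6.5 months.
- Gap from month 12 to month 24: 12 months, or 10 to 14 with both ±30-day windows.

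**3. Simulation.** 40 patients, exponential PFS, 600 or more trials per setting, scans as in step 2. A progression is dated at the next scan unless found clinically, 0.5 to 1 month after onset. All events are treated as progressions. Deaths without progression would be dated exactly and would shrink the error.

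| True median (months) | Found clinically | Typical KM median, exact dating | Typical KM median, plan's schedule | Shift |
|---|---|---|---|---|
| 12 | 0% | 11.6 | 12.9 | +1.3 |
| 12 | 50% | 11.4 | 12.6 | +1.2 |
| 13 | 0% | 12.5 | 23.1 | +10.6 |
| 13 | 50% | 12.5 | 13.7 | +1.2 |
| 13 | 80% | 12.3 | 13.1 | +0.8 |
| 15 | 0% | 14.3 | 23.5 | +9.2 |
| 15 | 50% | 14.7 | 18.2 | +3.5 |
| 18 | 0% | 17.5 | 24.0 | +6.5 |
| 18 | 50% | 17.2 | 23.1 | +5.9 |
| 18 | 80% | 17.5 | 19.7 | +2.2 |

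The typical shift at a true 12 months hides instability. The share of trials reporting 20 months or more is about 42% with scans only (42% to 46% over repeat runs), about 10% with half found clinically and 2% to 3% with 80%. For true medians of 6 to 10 months, the scans-only shift is 2.0 to 3.9 months.

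**4. PFS at fixed times, true median 12 months.**
- Month 18: true 2^(-18/12) = 0.35; estimated 0.50 (scans only) or 0.43 (half clinical).
- Month 12.0: true 0.50; estimated 0.59 (scans only), because many month-12 scans fall after that date.
- Month 24.0: true 0.25; estimated 0.36 (scans only).

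**5. Follow-up length.** Two years after the end of therapy gives 24 + 4.5 to 24 + 7.2 = 28.5 to 31.2 months per completer, against about 24 in the synopsis. With accrual this is 52.5 to 55.2 months (4.4 to 4.6 years), against about 4 years stated.

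**The case against.** A reader might infer that every PFS date will be a visit date and that the median will be wrong by about a year. The documents do not support that. Off-schedule assessment is allowed, research blood is collected at progression or relapse, and PFS runs to the time of progression, not to a visit. Scans-only detection is therefore an assumption. An error near a year needs a true median just past month 12 and almost no clinical detection. With half found clinically, a true 13 reads about 13 to 14. This stands, and it limits the size of the point.

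The exponential shape can also be challenged. Section 2.1.1 gives 3-year event-free survival of 31%, whereas an exponential with a 12-month median gives 2^(-3) = 12.5%. A Weibull through 50% at 12 months and 31% at 36 months (using event-free survival as a proxy) has shape ln(ln 0.31 / ln 0.50) / ln 3 = 0.48 and a true 18-month PFS of 43%. The 18-month bias then falls from 15 to 7 points (scans only) and from 7 to 4 (half clinical). The bias is smaller but has the same sign.

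PFS is secondary, with no hypothesis or power attached, and scan frequency in a 40-patient single-arm trial is a design choice. That is fair, so the remedy should add no scans.

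A reader might also infer that the two follow-up lengths cause the dating error. They do not. They are also partly reconcilable, because footnote j limits only the Active part and Survival Follow-up could run on. The synopsis's 24 months of participation and 4 years of study duration still do not fit.

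**Conclusion.** The point holds in a limited form. After the post-treatment scan, progression-free patients have disease status scheduled only at months 12 and 24, and the existing twice-yearly review does not reach them in between. Kaplan-Meier PFS between those months is biased upward to the extent that progressions are found only at scans. The documents do not give that extent.

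Under the exponential assumption, the typical median shift is about 1 month at a true 12 months, with a sizeable chance of a grossly late median if clinical detection is rare. At a true 18 months the shift is about 6 months with none or half found clinically and about 2 months with 80%. The two-stage CR rule is untouched. The follow-up length is a separate inconsistency of about 4.5 to 7 months per completer, affecting how long patients are followed and not how progression is dated.

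**What to change.** 1. **Record review.** Extend the existing twice-yearly record review to participants in Active Follow-up, capturing disease status and the date of first documented progression.
2. **Dating rule (11.3 and 12.6).** Date clinically found progressions at first documentation. Treat those first found at a scheduled scan as interval-censored between the last progression-free assessment and that scan. Censor at the last disease assessment.
3. **Reporting.** Give PFS at 12 and 24 months from the interval-censored estimate, or with scheduled scans assigned to their nominal month. Do not read Kaplan-Meier at exactly 12.0 and 24.0 months. Reading it at month 25 is no remedy either: if patients are censored at their own month-24 scan, the error reverses. Show Kaplan-Meier alongside. Give the median as a range when it falls inside the month 12 to 24 interval, because the interval-censored estimator cannot place events within it.
4. **Follow-up length.** Separately, reconcile the length and its starting point across Section 5.11, the calendar and the synopsis.

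The cost is a few chart reviews per patient by a method already in the protocol, plus one added analysis. The reported PFS may be lower and less precise.
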